3.3. Study Treatment

Subjects will be given a dose of 0.58 mg of EN3835 or placebo per treatment session for up to 3 treatment sessions at least 21 days apart (the Day 1, 22, and 43 Visits).

The injection concentration for each treatment visit is outlined in Table 3 below.

Table 3:Study Treatment

Cohort	Route of Administration	Number of Injections at Each Treatment Visit	Dose at Each Treatment visit (mg)	Number of Treatment Visits	Total Dose Administered (mg)
EN3835	Pericapsular (periarticular) Injection	1	0.58	3	1.74
Placebo	Pericapsular (periarticular) Injection	1		3	

3.4. Dose Interruption

All eligible subjects will receive their first dose of study treatment on Day 1. At each subsequent treatment visit (the Day 22 and 43 Visits) each subject will be evaluated to determine if they can continue treatment.

Subjects that have all 5 measurements of AROM and PROM (forward flexion, internal rotation, external rotation, abduction, and shoulder extension) of the affected shoulder that are > 90% of the baseline contralateral shoulder ROM and have an adapted ASES function subscale score of > 40 in the affected shoulder should not be dosed unless the investigator believes that the clinical benefit outweighs the risk.

Subjects who are not treated at the Day 22 Visit will continue in the study and will be reassessed at the Day 43 Visit and may be treated based on these assessments and investigator discretion. Subjects who are not treated at the Day 22 and/or Day 43 Visits will complete all other activities required for those visits and are also expected to complete the Day 64 and Day 95 Visits.

3.5. Determination of Sample Size

A post hoc analysis was conducted using a subgroup of AUX-CC-871 subjects who were rated with moderate/severe AC based on baseline MRI images. This subgroup displayed a notable treatment effect (EN3835 vs placebo) on the pain and composite components of the adapted ASES questionnaire. This subgroup also displayed a treatment effect trend for the functional component of the adapted ASES. Given this result, the sample size calculation is based on the mean and SD found in this subgroup for the adapted ASES composite score on Day 95. Given a mean change from baseline value in adapted ASES composite score at Day 95 of 38.6 for the EN3835 group and 27.6 for the placebo group with an SD of 21.6, a sample size of approximately 142 subjects would be required given a 1:1 randomization and a type I error of

0.05 with a power of 85%. With an expected drop-out rate of approximately 20%, 180 subjects (90 EN3835 and 90 placebo) should be dosed to ensure 142 complete the study.

3.6. Medical and Surgical History

A medical and surgical history of the subject will be taken during the Screening Visit. Medical history will include relevant diagnoses and procedures/therapies with onset/resolutions dates.

Medical history will include a review of the following systems: general, dermatological, respiratory, cardiovascular, gastrointestinal, genitourinary, gynecological, endocrine, musculoskeletal, hematological, neuropsychological, immune (allergies), and head, eyes, ears, nose, and throat. Historical and current medical conditions, including date of last menstrual period for female subjects, with onset/resolutions dates will be recorded.

In addition, any history or current collagen mediated disorders (including but not limited to Garrod's pads, Dupuytren's nodules, plantar nodules, Peyronie's disease, AC of other joints, etc) will be recorded (the current AC episode will not be recorded on the medical history case report form [CRF] - see next section).

Surgical history will include a review of all surgical procedures completed in the prior 5 years and any surgery completed at any time in the affected shoulder.

3.7. Adhesive Capsulitis History

A history of all past episodes of AC of the shoulder will be recorded at the Screening Visit. Details of each past episode to be collected include: the affected shoulder (right or left), onset date, resolution date, and any procedures or medical treatments provided.

In addition, the history of the current AC episode in the affected shoulder (right or left), onset date of symptoms, and determination of idiopathic or traumatic AC will be recorded at screening.

3.8. Substance Use

History of tobacco and alcohol use will also be taken during screening and the following information will be recorded:

- Type of substance (Alcohol/Tobacco).
- History of usage (Never/Currently/Former).
- Number of years the product was used (for current or former users).
- Stop date of using the product (for former users).

3.9. Prior and Concomitant Medications and Nondrug Therapies

Any medications and nondrug therapies (eg, blood transfusions, oxygen supplementation, physical therapy, etc) taken during the study or within 90 days prior to the Screening Visit will be recorded.

In addition, all prior medications and nondrug therapies for AC will be recorded.

3.10. Prohibited Medications

To be eligible for the study, subjects will agree not to use pain medications for the duration of the study period and for 2 weeks prior to the Screening Visit. Pain medications include, but are not limited to:

- opioids (eg, codeine, heroin, hydrocodone, hydromorphone, morphine, oxycodone, methadone, buprenorphine),
- cannabis.

Note: NSAIDs (ibuprofen, etc) and Tylenol (acetaminophen) are allowed.

In addition, the following medications or nondrug therapies will not be permitted during the study (from the Screening Visit through the Day 95 Visit):

- Anticoagulant or antiplatelet medication (except ≤ 150 mg aspirin daily).
- Any other medications or nondrug therapies for the affected shoulder other than those outlined in this protocol.
- Any collagenase treatments (eg, Santyl ointment, XIAFLEX) other than study treatment.
- Any investigational product, device, or procedure administered as part of a research study other than the treatment in this study.

If any prohibited medication is taken during the study, all pertinent information will be recorded.

3.11. Passive External Rotation at 0°, 45°, and 90° of Abduction

Passive external rotation at 0° , 45° , and 90° of abduction will be measured in both shoulders using a goniometer at screening in the supine position. In the event that 45° and 90° cannot be achieved due to pain or restriction in the affected shoulder, the amount of external rotation available at maximum attainable abduction ROM is permissible as the second and third measurements.

3.12. Hand Dominance

The subject's self-reported hand dominance will be recorded at screening.

3.13. Supervised In-office Physical Therapy

All subjects will undergo a standard supervised in-office physical therapy regimen. The physical therapy regimen will consist of 2 sessions per week for 2 weeks with a minimum of 2 days between each session starting 7 days after each study treatment until the next scheduled injection and until the Day 64 Visit. In-office physical therapy will last approximately 30 to 60 minutes. Subjects will be provided with verbal and hands-on instructions for the exercises to be completed. Physical therapists will follow the standard physical therapy regimen found in the Study Operations Manual.

3.14. Home Exercises

Study personnel will train each subject how to conduct a standard set of home exercises and provide each subject with a set of instructions and any necessary equipment (ie, pulleys) to complete the home exercises. These home exercises should be performed by each subject at least 2 times per day and no more than 3 times a day. Home exercises will begin 3 days after each study treatment and will end at the Day 95/ET Visit. In-office PT will count as 1 of the home exercise sessions on PT days.

Subjects will document their home exercise completion and frequency using a diary. The site will train the subject on the use of the diary and will review the diary at visits specified in the Schedule of Activities (SoA) (Table 2) to ensure compliance.

3.15. Efficacy Assessments

3.15.1. Adapted American Shoulder and Elbow Surgeons Standardized Shoulder Form (ASES)

The adapted ASES is a questionnaire to assess AC patient rated shoulder pain and function that has been modified from the ASES Standardized Shoulder Form.(2,3) All subjects will complete the adapted ASES at times outlined in the SoA (Table 2).

The adapted ASES is a self-administered patient reported outcome measure, comprised of 2 subscales: pain subscale and function subscale.

Pain subscale: Numeric rating scale about pain in the affected shoulder on the day of assessment. Scale ranges from 0 (No pain at all) to 10 (Pain as bad as it can be).

Table 4:ASES: Pain Subscale

					R	espons	es				
Question	0	1	2	3	4	5	6	7	8	9	10
How bad is the pain in your affected shoulder today?											

Function subscale: This scale consists of 10 activities of daily living where the subject is asked to indicate on a 4 point ordinal scale their ability to do the activity with the affected arm.(4) Scale ranges from 0 to 3.

The responses are: 0 =Unable to do; 1 =Very difficult; 2 = Somewhat difficult; 3 =Not difficult.

	Question	R	esponses for A	ffected Shoul	der
No.	Is it difficult for you to	0	1	2	3
1	Put on a coat				
2	Sleep on your painful or affected side				
3	Wash back/do-up bra in back				
4	Manage toileting				
5	Comb hair				
6	Reach a high shelf				
7	Lift 10 lbs. (4.5kg) above shoulder				
8	Throw a ball overhand				
9	Do usual work				
10	Do usual sport/leisure activities				

Table 5:ASES: Function Subscale

3.15.2. Range of Motion (ROM)

PROM and AROM will be measured for the affected and contralateral shoulder at times specified in the SoA (Table 2) using a goniometer. The below range of motion measurements will be recorded:

- Forward flexion.
- Internal rotation.
- External rotation.
- Abduction.
- Shoulder extension.

The unit to measure PROM and AROM is degrees (°).

In addition, Hand Behind the Back (HBB) assessment will be performed for active internal rotation. The response for HBB assessment will be free text with no unit.

3.15.3. Pain Upon Movement (PUM)

The PUM Scale is a single item 11-point numerical rating scale of pain that asks subjects to rate the pain in their affected shoulder after AROM forward flexion, internal rotation, external rotation, abduction, and shoulder extension on a scale from 0 (No pain at all) to 10 (Pain as bad as it can be).

	Responses										
Question	0	1	2	3	4	5	6	7	8	9	10
When you move your arm to the point where pain limits your movement in the affected shoulder (forward and backwards circles keeping elbow straight, lifting arms out to the side, reaching your arm behind your back as if you were getting something out of your pocket, positioning your arms as if you were carrying serving trays keeping your elbows glued to your sides, and extending your arms straight behind you) please rate your worst pain on a scale of 0-10 when you do these movements with your affected shoulder.											

All subjects will complete the PUM at times outlined in the SoA (Table 2).

3.15.4. Patient-reported Global Severity of Adhesive Capsulitis

The Patient-reported Global Severity of Adhesive Capsulitis is a single item 11-point numerical rating scale that asks subjects to rate the overall severity of their AC symptoms on a scale from 0 (No severity) to 10 (Severe as can be).

Table 7: Patient-reported Global Severity of Adhesive Capsulitis Scale

	Responses										
Question	0	1	2	3	4	5	6	7	8	9	10
What is the severity of your frozen shoulder in the last 24 hours?											

All subjects will complete the Patient-reported Global Severity of Adhesive Capsulitis scale at times outlined in the SoA (Table 2).

3.15.4.1. Patient-reported Change in Severity of Adhesive Capsulitis

The Patient-reported Change in Severity of Adhesive Capsulitis is a questionnaire that asks subjects if their AC symptoms are "Better, About the Same, or Worse" since the last time the questionnaire was administered.

Subjects who report that their symptoms are better or worse are then asked to rate the change in their symptoms on a 7-point ordinal scale.

			Responses
No.	Question	Numeric	Description
1	Have there been any changes in overall severity of	-1	Worse (Complete Question 2)
	your frozen shoulder since you started the study?	0	About the same (Stop)
		1	Better (Complete Question 3)
2	How much worse would you say the overall severity of	0	Almost the same, hardly worse at all
	your frozen shoulder is since you started the study?	-1	A little worse
		-2	Somewhat worse
		-3	Moderately worse
		-4	A good deal worse
		-5	A great deal worse
		-6	A very great deal worse
3	How much better would you say the overall severity of	0	Almost the same, hardly better at all
	your frozen shoulder is since you started the study?	1	A little better
		2	Somewhat better
		3	Moderately better
		4	A good deal better
		5	A great deal better
		6	A very great deal better

 Table 8:
 Patient-reported Change in Severity of Adhesive Capsulitis Scale

All subjects will complete the Patient-reported Change in Severity of Adhesive Capsulitis questionnaire at times outlined in the SoA (Table 2).

3.15.5. Subject Satisfaction with Treatment

Subjects will rate their satisfaction with treatment on a 7-point Likert scale from Very Dissatisfied to Very Satisfied at times specified in the SoA (Table 2).

			Responses
No.	Question	Numeric	Description
1	In your treated shoulder, how satisfied are you with the relief of pain now compared to the pain prior to treatment?	3	Very Satisfied
		2	Satisfied
		1	Somewhat Satisfied
		0	Neither Satisfied nor Dissatisfied
		-1	Somewhat Dissatisfied
		-2	Dissatisfied
		-3	Very Dissatisfied
2	In your treated shoulder, how satisfied are you with the	3	Very Satisfied
	relief of stiffness now compared to the stiffness prior to treatment?	2	Satisfied
		1	Somewhat Satisfied
		0	Neither Satisfied nor Dissatisfied
		-1	Somewhat Dissatisfied
		-2	Dissatisfied
		-3	Very Dissatisfied

Table 9:Subject Satisfaction Prior to Receiving Treatment

Table 10: Subject Satisfaction Compared to Better Shoulder

		Responses		
No.	Question	Numeric	Description	
1	Compared to your better shoulder, overall how satisfied	3	Very Satisfied	
	are you with the relief of pain in your treated shoulder?	2	Satisfied	
		1	Somewhat Satisfied	
		0	Neither Satisfied nor Dissatisfied	
		-1	Somewhat Dissatisfied	
		-2	Dissatisfied	
		-3	Very Dissatisfied	
2	Compared to your better shoulder, overall how satisfied	3	Very Satisfied	
	are you with the relief of stiffness in your treated shoulder?	2	Satisfied	
		1	Somewhat Satisfied	
		0	Neither Satisfied nor Dissatisfied	
		-1	Somewhat Dissatisfied	
		-2	Dissatisfied	
		-3	Very Dissatisfied	

3.15.6. Investigator Assessment of Improvement with Treatment

Investigators will provide their assessment of improvement with treatment for each subject using a 7-point Likert scale from Very Much Worse to Very Much Improved at times specified in the SoA (Table 2).

			Responses
No.	Question	Numeric	Description
1	At the follow-up visit, please rate the degree of change	3	Very Much Improved
	in the severity of the subject's treated shoulder compared with screening	2	Much Improved
		1	Minimally Improved
		0	No Change
		-1	Minimally Worse
		-2	Much Worse
		-3	Very Much Worse

 Table 11:
 Investigator Assessment of Improvement with Treatment

3.15.7. Magnetic Response Imaging (MRI) and X-rays

An X-ray of the affected shoulder is required at screening unless there is a historic X-ray of the affected shoulder that was taken within 30 days of the Screening Visit.

MRIs of the affected shoulder will be performed for all subjects at Screening and Day 95 and of the contralateral shoulder at the Screening Visit only.

Subjects should complete all other screening activities prior to the MRIs required at screening and must meet the entry criteria.

3.16. Safety Assessments

Virtual visits are allowed to assess safety during any COVID-19 interruption.

3.16.1. Adverse Events

All adverse events (AEs) will be recorded from the time informed consent is signed through the Day 95/ET Visit, or for 28 days after the last dose of study treatment for those who early terminate.

Conditions existing prior to screening will be recorded as part of subject's medical history.

3.16.1.1. Adverse Events (AE)

An AE is any unfavorable or unintended change in body structure (signs), body function (symptoms), laboratory result (eg, chemistry, ECG, X-ray, etc), or worsening of a pre-existing condition associated temporally with the use of the study medication whether or not considered related to the study medication. This would include AEs resulting from concurrent illness, reactions to concurrent medication use, or progression of disease states (excluding the disease under study). A condition present at baseline that worsens after initiation of study treatment will be captured as an AE; the onset date will be the date the event worsened.

25-April-2022

3.16.1.2. Serious Adverse Events (SAEs)

SAEs are those AEs that meet any of the following criteria:

- Results in death.
- Life-threatening event.
- Results in or prolongs an inpatient hospitalization.
- Results in permanent or substantial disability.
- Is a congenital anomaly or birth defect.
- Any important medical event that may jeopardize the subject or may require medical intervention to prevent one of the outcomes listed above.

3.16.1.3. Adverse Events of Special Interest (AESI)

AESIs for this study include:

- Bruising, ecchymosis, hematomas, and contusions that occur remote to the site of treatment administration.
- Any hypersensitivity reactions.

These events will be reported as AEs in the electronic case report form (eCRF). All AESIs will be evaluated for seriousness and severity. AESIs will be sponsor-defined by the AE preferred term prior to database lock.

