2.3. Benefit/Risk Assessment

Although a thorough benefit of EN3835 has not been fully established in the treatment of AC, the post hoc analyses from the previous phase 2b study (AUX-CC-871) and previous AC studies indicate that EN3835 should be further explored as a treatment. In addition, the lack of consensus regarding treatment of AC and the risks associated with surgical or drug treatment or with long-term corticosteroid use suggest that safe and effective treatments for this condition are needed.

In the most recent study of EN3835 in AC (AUX-CC-871), the most common (\geq 5% of subjects) treatment-related, treatment-emergent adverse events (TEAEs) were musculoskeletal pain (34.2%), contusion (28.7%), injection site pain (21.1%), ecchymosis (19.8%), injection site bruising (19.4%), localized edema (8.0%), and pruritus (5.1%). These events are similar to events reported in the clinical trials of EN3835 for the approved indications, and postmarketing safety data are consistent with the safety data reported in clinical trials.

Use caution when administering EN3835 so as not to inject intra-articularly. A single animal study indicated significant adverse events associated with intra-articular injection of EN3835. While the effect in humans is not known, intra-articular injection (misapplication) of EN3835 during treatment of AC must be avoided.

More information about the known and expected benefit, risks, and reasonably expected adverse events (AEs) can be found in the Investigator's Brochure (Endo, 2020).

Risks associated with the use of a local anesthetic include bruising, pain, tingling, blurred vision, dizziness, headache, muscle twitching, weakness, and continuing numbness. Local anesthetics can sometimes cause allergic reactions including hives, itching, and difficulty breathing. In rare cases, cyanosis can occur at the site of injection; and very rarely, use of a local anesthetic can lead to depressed central nervous system syndrome.

The baseline shoulder X-ray exposes subjects to a very low level of radiation. Extensive exposure to radiation can lead to cancer. Exposure to any radiation can harm an unborn fetus in a pregnant woman.

Risks associated with ultrasound are rare; however, subjects undergoing ultrasound may experience slight heating of tissues and the creation of cavitations (small pockets of gas) within the body. The long term effects of these events are unknown.

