8.3.7. Adverse Events of Special Interest

AESIs for this study include:

• Bruising, ecchymosis, hematomas, and contusions that occur remote to the site of treatment administration.

• Any hypersensitivity reactions.

These events will be reported as AEs in the eCRF. All AESIs will be evaluated for seriousness and severity. If any of these events meet the criteria for an SAE, they will also be reported as such using the procedure outlined in Section 10.3.

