• To assess the safety and immunogenicity of EN3835 for the treatment of AC of the shoulder.	 The proportion of subjects reporting each adverse event, treatment-emergent adverse event, adverse event of special interest, and serious adverse event. The change from baseline in vital signs and clinical laboratory values at each visit where these parameters are measured. The presence and titer levels of anti-AUX-I and anti-AUX-II antibodies and the presence of neutralizing antibodies at each visit where these parameters are measured.
Exploratory/Tertiary	
•	•

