4.8. Safety Parameters

4.8.1. Adverse Events

Adverse event verbatim terms as reported by the investigator will be mapped to system organ class (SOC) and preferred term (PT) using the Medical Dictionary for Regulatory Activities (MedDRA) dictionary. The dictionary version to be used will be defined in the DMP.

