6. STATISTICAL METHODS

6.1. General Methodology

All statistical tests, summary tables and data listings will be prepared using SAS version 9.3 or higher.

All statistical tests of efficacy parameters will be 2-sided with a significance level of α =0.05, unless specified otherwise. Statistical tests will be supported by presenting estimates and 95% confidence intervals (CI) for each treatment group.

Continuous data will be summarized using descriptive statistics (number of subjects [n], mean, SD, median, minimum, and maximum). Discrete data will be summarized using frequency counts and percentages. The denominator will be based on the number of subjects in the appropriate population.

For the purpose of display, the summary results will be rounded as follows:

- Minimum and maximum: Same number of decimal places as the raw data.
- Mean and Median: One more decimal place than the raw data.

- SD: Two more decimal places than the raw data.
- Percentages will be displayed with 1 decimal place precision. A zero count will be left blank.
- The standard form of a percentage change variable is 0 decimal places.

For categorical variables with missing values, a category documenting the frequency of missing values will be displayed in the summary tables.

Summary tables, subject listings, graphs and any supportive SAS output will include footnotes that will indicate:

- Date of data extraction.
- Date and time of output generation.
- SAS program name, including the path that generated the output.

When calculating percentages, the denominator will be based on the number of subjects with non-missing values. If the denominator is expected to change over time, then the denominator used to calculate the percentage will be based on the number of subjects with non-missing values at each visit. Any subject removed from an analysis will be noted at the bottom of the table along with the reason the subject was removed.

Empty summary tables will be presented with a note stating that "No Subjects Met Criteria."

Subject listings of all data from the eCRFs as well as any derived variables will be presented.

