7.10.2. Adverse Events

Proportion of subjects reporting at least 1 adverse event, treatment-emergent adverse event, adverse event of special interest, and serious adverse event will be compared for EN3835 to placebo treatment group using Fisher's exact test.

The null and alternative hypotheses for this test will be as below:

 H_0 : p1 = p2 (Proportion of subjects having an adverse event are equal in treatment groups) Vs

H₁: $p1 \neq p2$ (Proportion of subjects having an adverse event are unequal in treatment groups) Where,

p1: Proportion of subjects having adverse event in EN3835 treatment group.

p2: Proportion of subjects having adverse event in placebo treatment group.

Number and proportion of subjects with at least 1 adverse event, treatment-emergent adverse event, adverse event of special interest, and serious adverse will be summarized by treatment groups and in addition p value for treatment comparison will also be presented.

All AE summary tables will include only TEAEs, unless otherwise specified.

AEs will be summarized by SOC and PT. A subject will only be counted once per SOC and PT.

For AEs by severity grade (mild, moderate, severe), if a subject has multiple events occurring in the same SOC or same PT, then the event with the maximum intensity (ie, severe) will be counted.

For AEs by relationship to study drug, if a subject has multiple events occurring in the same SOC or same PT, the event with the highest association (ie, related) to study drug will be summarized.

AEs will be presented in decreasing order of the incidences at SOC level and within each SOC, in decreasing order of the incidences at the PT level.

An overall summary of AEs and AEs related to study drug will be presented and will include:

- Total number of TEAEs reported.
- Total number of TEAEs reported by severity.
- Total number of TEAEs of special interest.
- Subjects with any TEAE.
- Subjects with any TEAE of special interest.
- Subjects with any serious TEAE.
- Subjects with any severe TEAE.
- Subjects with no severe TEAEs, but at least 1 moderate TEAE.
- Subjects with no severe TEAEs, but at least 1 mild TEAE.
- Subjects with any TEAEs leading to drug interruption/withdrawal.
- Subjects with any TEAEs leading to study discontinuation.
- Subjects with any TEAEs resulting in death.

The following summary tables will be presented by SOC and PT:

- All TEAEs.
- Study drug related TEAEs.
- TEAEs by severity.
- Study drug related TEAEs by severity.

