- Study drug related TEAEs by treatment session
- Duration (1-7 days, 8-14 days, 15-21 days, > 21 days) of study drug related TEAEs.
- Serious TEAEs.

- TEAE of special interest.
- TEAE of special interest by severity.

Most common non-serious TEAEs by order of frequency (Most frequent, 2nd most frequent, and 3rd most frequent) will be summarized by PT. Most common non-serious AEs are those that at least 5% of the subjects reported at least once (using PT).

The following listings will be presented by subject:

- All AEs.
- AEs resulting in death.
- Non-fatal serious AEs.
- AEs resulting in drug interruption/withdrawal.
- AEs resulting in study discontinuation.

Refer to Table 16 for computation of duration of AEs.

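### The bruising AESI is defined by location, but the SAP identifies AESIs by preferred term, which often carries no location

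*SAP*

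**What the plan says.** Protocol 8.3.7 and SAP 3.16.1.3 give the same two AESI categories: any hypersensitivity reaction, and "Bruising, ecchymosis, hematomas, and contusions that occur remote to the site of treatment administration". The second is conditional on where the event occurs.

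SAP 3.16.1.3 then states how events will be identified: "AESIs will be sponsor-defined by the AE preferred term prior to database lock". SAP 4.8.1 explains where a preferred term comes from: the investigator's verbatim term is coded in MedDRA to a system organ class and preferred term. Neither section mentions a location variable, an investigator AESI flag or a case-level review.

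The result is used in several places. SAP section 2 makes it an endpoint: "The proportion of subjects reporting each adverse event, treatment-emergent adverse event, adverse event of special interest, and serious adverse event". SAP 7.10.2 tests it with Fisher's exact test: "Proportion of subjects reporting at least 1 adverse event, treatment-emergent adverse event, adverse event of special interest, and serious adverse event will be compared". The same section tabulates AESIs by system organ class and preferred term, and adds "TEAE of special interest by severity".

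Protocol 2.3 reports the treatment-related events seen in the previous adhesive capsulitis study. Three are bruising-type terms: contusion (28.7%), ecchymosis (19.8%) and injection site bruising (19.4%).

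**The concern.** The definition turns on a fact, remoteness, that the identification rule does not use. A preferred term can apply the definition only if the term itself names a site. Injection site bruising does, so a list can leave it out. Contusion and ecchymosis do not.

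If such terms are listed, ordinary bruising next to the injection can be counted and tested as remote bruising. If they are not listed, remote bruising coded to them drops out of the AESI analysis. Either way, the reported proportion and its p-value could describe something other than the category the protocol singled out for special attention.

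**Working it through.** The plan states no figure to reproduce on this point, so the check compares the texts and then gives one illustration of scale.

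**1. What the definition needs.** Two facts per event: that it is of bruising type, and that it is remote from the injection (Protocol 8.3.7, SAP 3.16.1.3).

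**2. What the rule supplies.** Only the preferred term (SAP 3.16.1.3), derived from the verbatim term (SAP 4.8.1).

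**3. Whether the term can carry the second fact.** Of the three bruising-type terms in Protocol 2.3, one names a site (injection site bruising) and two do not (contusion, ecchymosis).

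**4. Consequence for a term without a site.**

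| Term on the AESI list? | Remote events | Local events | Error-free only if |
|---|---|---|---|
| Yes | counted correctly | counted wrongly | all its events are remote |
| No | missed | left out correctly | all its events are local |

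Nothing in the documents supports either condition in the last column.

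**5. Whether another step restores location.** SAP 6.1 promises that "Subject listings of all data from the eCRFs as well as any derived variables will be presented". Listings would show a location if one was recorded, but they do not correct the derived AESI flag, or the Fisher test based on it.

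**6. Scale, as illustration only.** Inputs are the two rates from Protocol 2.3 and 90 subjects per arm from Protocol 9.1. The rates are for treatment-related events, and the protocol does not say which arm they describe. Applying them to one arm of 90 is an assumption.

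- Contusion: 0.287 × 90 = 25.8 subjects.
- Ecchymosis: 0.198 × 90 = 17.8 subjects.
- At least one of the two, full overlap: 28.7%, or about 26 subjects.
- At least one of the two, no overlap: 28.7% + 19.8% = 48.5%, and 0.485 × 90 = 43.7, or about 44 subjects.

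If both terms were listed, these 26 to 44 subjects would be flagged wherever the bruise was. How many would be flagged correctly depends on the share with a remote event, which is unknown. With an assumed share of 5%, the true proportion from these terms would be 0.05 × 28.7% = 1.4% to 0.05 × 48.5% = 2.4%. With an assumed 50%, it would be about 14% to 24%.

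These figures do not bound or estimate the misclassification. AESIs are not restricted to treatment-related events, and Protocol 2.3 gives no hematoma rate. A subject with another true AESI is counted correctly whatever happens to the bruise.

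**The case against.** The strongest reply is that the two sentences in SAP 3.16.1.3 are compatible. The term rule follows directly after the bullet with the remoteness condition, and nothing says it replaces that bullet. The sponsor may intend to choose terms and apply them within the definition. Protocol 8.3.3 also follows nonserious AESIs beyond the limit set for other nonserious events, which presupposes that sites recognise an AESI, and hence its remoteness, when it happens. A location field could exist in the eCRF, the Data Management Plan or the SAP Module 2 shells, none of which can be seen here. Finally, injection site bruising is listed separately from contusion and ecchymosis, so local events may already be coded to the site-specific term.

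Some of this stands. The defect may be incomplete wording rather than a wrong intention, and the documents do not show that any local event was coded to a term without a site. They do not show the opposite either. No visible text states a step that applies location, and the SAP does not say that it uses site recognition or a location field. Fixing the list before lock limits post hoc choice of terms but does not supply the missing fact.

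It is also fair that the consequence is narrow. Because AESIs are tabulated by preferred term, a reader can see which terms drive the count, though not which of those events were remote.

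**Conclusion.** The concern holds. As written, the identification rule does not implement the definition of the bruising AESI, so the AESI proportion and its between-arm test may be wrong in either direction. The size of the error and its effect on the comparison cannot be derived, because the documents give no local/remote split, term list or placebo rate.

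The scope is limited to the AESI endpoint, its Fisher test and the AESI tables. The overall TEAE and preferred-term tables, the hypersensitivity AESI and the primary endpoint are unaffected. The conclusion assumes that no unseen document adds a location step. It should be corrected, with medium confidence that the practical effect is material.

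**What to change.** In SAP 3.16.1.3, make the preferred-term list a screen for bruising-type events, including hematoma. Then classify each screened event as remote or local from the verbatim term, any recorded site or a query to the site. Derive the bruising AESI flag from that classification. Keep the term-based rule for hypersensitivity.

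The study medical monitor can do this in a treatment-blinded review before database lock. SAP 4.4.1 already gives the monitor a comparable task for adhesive capsulitis treatments. Protocol 6.3 blinds sponsor personnel other than clinical supplies staff, but the documents do not say whether the monitor is among them, so the SAP should confirm the monitor's blinding. A written criterion for what counts as remote would make the classification reproducible, since neither document defines it.

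The cost is SAP wording plus one blinded listing review of bruising-type events in both arms. The number of events to review cannot be derived from the documents. If the eCRF has no adverse event location field, the review rests on verbatim terms and needs more queries.
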